### **6.2.7 Rationale for Control Condition**

The selection of our control group was influenced by several factors. There are currently only 20 Prisma Health primary care clinics that have not received EIMG onboarding and activation and that are within 15 miles or less of a participating community PA facility. There are no other equivalent Prisma Health primary care clinics to serve as matched controls (i.e., via a stepped wedge design). We are then left with two groups of clinics to serve as controls. The first of these is using a within-clinic design and comparing patient health outcomes before and after the dissemination of the initial EIMG Instructional Video. Secondly, from past experiences, we anticipate that several of the 20 clinics will choose not to adopt EIMG and/or will be non-responsive to our invitation. As one of our study aims, we will evaluate contextual factors and differences between adopting and non-adopting clinics. Clinics that do not adopt EIMG will not be 'activated' and can therefore serve as control clinics, particularly when evaluating patient-level outcomes, as none of their patients will have had the opportunity to participate in EIMG.

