## 7.0 STUDY POPULATION

### 7.1 Prisma Health - Clinic Eligibility

As the unit of randomization, we will offer the opportunity to adopt EIMG to 20 Prisma Health primary care clinics that have not yet implemented EIMG. The department chairs for Internal and Family Medicine (Drs. [name] and [name]) have provided their support for EIMG expansion across these primary care clinics.

Eligibility criteria for clinics to participate in this study include the following:

- Prisma Health primary care clinics (i.e., family or internal medicine) located in the Upstate of South Carolina
- Have not received EIMG onboarding or activation in the past;
- Consist of at least two attending providers;
- Be located 15 miles or less from a participating community PA facility.

All potentially eligible Prisma Health primary care clinics were geographically coded to determine the distance to the nearest participating community PA facility. Clinics >15 miles will be ineligible for study participation as previous research consistently demonstrates that engagement in leisure time PA and enrollment in fitness centers is negatively correlated with distance to PA destinations.

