### 12.2 Statistical Methods for Primary Analysis

Clinic level nominal characteristics will be summarized as count and proportion; quantitative characteristics (e.g., patient census, provider census, etc) will be summarized as using the median and interquartile range. Patient level data will be summarized monthly by clinic using count and proportions for categorical data and mean (standard deviation) or median (interquartile range) as appropriate.

Clinic level characteristics will be compared between adopting and non-adopting clinics to look for indicators that may be leveraged to improve the adoption of EIMG into the patient care workflow. Similarly, there may be providers within participating clinics that choose not to adopt EIMG (refer eligible patients to the physical activity program); characteristics of the providers will be compared to look for ways to adopt / improve EIMG referral.

The primary endpoint will be analyzed on an intent-to-treat basis. This means that clinics will be analyzed according to their agreement to adopt regardless of their subsequent participation. For analyses at the patient level, patients within EIMG-adopting clinics that receive referrals will be analyzed as EIMG participants regardless of their subsequent actions / participation. Referred patients will be considered as part of the “EIMG group” even though they may not be perfectly compliant or follow the prescribed dose of exercise in the physical activity program.

The effect of EIMG on outcomes for overall reach will be analyzed using generalized linear mixed models (GLMM). The use of the GLMM accounts for the variability between clinics (random intercept) and the random effect of time within each clinic. The right-hand side of the model will have the same form. The left-hand side of the model may require the use of different link functions. Our experimental units are the clinics themselves with the observational units being the EIMG eligible patients nested within each clinic. The analytical models will have the following form:

$$g(Y_{ijk}) = (\beta_0 + \mu_{0i}) + \beta_1 EIMG_j + (\beta_2 + \mu_{2i})X_i + (\beta_3 + \mu_{3k})T_k + (\beta_4 + \mu_{4ijk})EIMG_j T_k + e_{ijk}$$

[figure not shown]

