$E_{ijk}$  equals 1 if patient “i” in the episode at clinic “j” in the “k-th” month after study initiation was referred to EIMG, 0 otherwise;  $X_{ijk}$  represents patient-specific baseline demographic, clinical, and socioeconomic factors,  $L_j$  are a series of binary variable for each Prisma clinic “j”,  $M_k$  is a count variable representing the number of months since the beginning the study that contains patient “i’s” index date, and  $C_{ijk}$  equals 1 if the episode occurred in a period in which the clinic “j” received or had previously received EIMG activation, 0 otherwise. The parameters  $\omega_j$ ,  $u_k$ , and  $\epsilon_{ijk}$  represent the model random effects associated with site “j”, month “k”, and patient “i”, respectively. We will estimate equation (1) using a generalized linear mixed model. The estimate of parameter  $\beta_4$  equals the effect of standardized EIMG training on the probability of the patient within the episode being referred to EIMG. Variables within  $X_{ijk}$  will include patient history of EIMG use. Our stepped wedge design will enable us to directly control for unmeasured factors associated with site and time. Secondary analyses will assess differences in the impact of standardized EIMG training by stratifying by eligible conditions (i.e., overweight/obese, hypertension, type 2 diabetes).

While EIMG activation will be randomly assigned to clinics using the stepped wedge design, actual EIMG referral decisions will remain at the discretion of provider and patient. As a result, referral decisions for some patients will be “non-compliant” at the clinical level. Providers may refer patients into EIMG based on factors unmeasured by the researcher that are related to study outcomes which can confound estimation of the effect of EIMG on study outcomes. With non-compliance, it is problematic to use “as treated” EIMG referral variation to assess the effects of EIMG referrals on study outcomes. Instrumental variable (IV) methods using randomized EIMG activation as an “instrument” will be used to avoid confounding problems. In this scenario IV estimation will yield consistent estimates of the effect of EIMG referral on study outcomes for the subset of patients whose referrals are responsive to the randomized clinical-level EIMG activation. This is known as the Complier Average Causal Effect (CACE). The CACE model is specified as:

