$$(3) \quad Y_{ijk} = \alpha_0 + \alpha_1 \cdot X_{ijk} + \alpha_2 \cdot L_j + \alpha_3 \cdot M_k + \alpha_4 \cdot \hat{E}_{ijk} + \rho_j + \tau_k + \vartheta_{ijk}, \text{ where}$$

$\hat{E}_i$  equals the *predicted probability* of that patient “i” is referred to EIMG from equation (2); and the other variables defined as in equation (2). The parameters  $\rho_j$ ,  $\tau_k$ , and  $\vartheta_{ijk}$  represent the random effects associated with site “j”, month “k”, and patient “i”, respectively. The estimated parameter  $\alpha_4$  on  $\hat{E}_{ijk}$  is the CACE or the average treatment effect for patient subset whose EIMG referral was influenced by EIMG activation at the clinic.  $C_{ijk}$  in equation (2) serves as the “instrument” and only the portion of variation in  $\hat{E}_{ijk}$  stemming from  $C_{ijk}$  is used to estimate  $\alpha_4$ . Because  $C_{ijk}$  will be randomly assigned, EIMG referral variation stemming from this assignment will be independent of unmeasured confounding variables. Two-stage least squares (2SLS) IV estimators will be used to estimate the effects of EIMG referrals induced by clinical-level EIMG activation on study outcomes. For each study outcome, equation (2) will serve as the first stage

equation of 2SLS, and second stage model will be equation (3). Because our expected sample sizes will be greater than 500 *our 2SLS estimates will be distributed normally via the central limit theorem regardless of the distribution of the underlying error term.* Each 2SLS model will be estimated with robust standard error methods appropriate for 2SLS models using STATA to account for error structure in equation (3).

Define  $\alpha_{4C}$  as the 2SLS estimate when episode healthcare cost is the dependent variable in equation (3) and  $\alpha_{4H}$  as the 2SLS estimate when a health outcome change is the dependent variable in equation (3). Combining these estimates with the estimates of average patient EIMG training costs from Section F3.2 yields the following cost-effectiveness ratio of EIMG relative to standard care:

$$(4) \text{ EIMG Cost Effectiveness Ratio} = \left[ \frac{(\text{EIMG Training Costs per Patient} + \alpha_{4C})}{\alpha_{4H}} \right]$$

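### An expected count above 500 does not make the 2SLS estimates normal: the instrument is set by clinic and period over at most 20 clinics, and the plan names no clustering level or first-stage check

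*Combined protocol and SAP*

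**What the plan says.** Section 12.5.5 estimates the effect of EIMG referral on episode cost (alpha_4C) and on each health outcome (alpha_4H) by 2SLS. The instrument C equals 1 if the clinic "received or had previously received EIMG activation, 0 otherwise". Equations (2) and (3) both contain clinic indicators, a month count, and site and month random terms.

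On inference the section makes two statements. The first is "Because our expected sample sizes will be greater than 500", from which it concludes that "our 2SLS estimates will be distributed normally via the central limit theorem regardless of the distribution of the underlying error term". The second is "Each 2SLS model will be estimated with robust standard error methods appropriate for 2SLS models", in Stata, so as to account for the error structure of equation (3). It gives no clustering level, small-cluster correction, first-stage F, weak-instrument method or derivation of the 500.

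Other sections bear on this:
- Section 7.1: "we will offer the opportunity to adopt EIMG to 20 Prisma Health primary care clinics that have not yet implemented EIMG".
- Section 6.2.7: "we anticipate that several of the 20 clinics will choose not to adopt EIMG and/or will be non-responsive to our invitation". Patients of non-activated clinics cannot take part in EIMG.
- Section 8.1: all clinics are invited at the same time.
- Section 12.2: "Our experimental units are the clinics themselves".
- Section 12.3: referral is assumed to run from 0.1% to 1% after the video and to reach 4% at month 8.

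**The concern.** A central limit argument for 2SLS needs enough independent information in the instrument and a first stage that is clearly non-zero. Here C takes one value for every episode in a clinic and period and switches once for adopting clinics. The independent information is therefore closer to the number of clinics than to the number of patients. The first stage is the jump in referral at activation, which the plan itself puts at a few percent or less. The count of 500 addresses neither point.

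The estimates alpha_4C and alpha_4H are the inputs to the cost-effectiveness ratio in equation (4), and Section 5.3 hopes the economic results will inform coverage and adoption decisions. Equation (4) is also estimated separately by diagnosis, and the health outcomes need a recorded value at a visit in the Outcome Period. The number behind any one model can therefore be well below the total.

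**Working it through.** The figure of 500 has no derivation, so there is nothing to reproduce. The check takes it as a floor and asks what holds there and at larger counts.

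**Inputs from the documents.** 20 clinics; one activation date; no referral without activation; clinic indicators and a linear month term. Both profiles in Section 12.3 average near 2% over the eight months. The step profile gives [(0.1+1)/2 + (3+4)/2]/2 = 2.0%. The accelerated profile gives [(0.1+1)/2 + (2+4)/2]/2 = 1.8%. The check uses p = 1%, 2% and 4%.

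**Assumptions not in the documents.** Equal clinic sizes; 8 months before and 8 after activation; the referral rate applies per episode; 10 or 15 adopters unless stated; correlation of outcomes within a clinic and period (ICC), beyond constant clinic differences, of 0.01 or 0.03; error correlation 0.3 between the two stages (0 and 0.8 gave the same pattern at N = 500).

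**Step 1. First stage without other terms.** With q the share of episodes under activation, F ≈ 1 + N(1−q)p/(1−p). At N = 500 and q = 0.5:
- 1%: 1 + 250 × 0.0101 = 3.5
- 2%: 1 + 250 × 0.0204 = 6.1
- 4%: 1 + 250 × 0.0417 = 11.4

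At q = 0.25 the values are 4.8, 8.7 and 16.6. Expected referrals at q = 0.5 are 250 × 0.01 = 2.5 to 250 × 0.04 = 10.

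**Step 2. With clinic indicators and month trend.** Let s be the share of clinics adopting, so q = s/2. The squared correlation of a step after month 8 with month 1 to 16 is 2²/(21.25 × 0.25) = 0.753. The variance of C left after these terms is V = 0.25s(1 − 0.753s), and F ≈ 1 + N[p/(1−p)](V/q).
- s = 0.5: V = 0.078, V/q = 0.312
- s = 0.75: V = 0.082, V/q = 0.218

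| N | p = 1% | p = 2% | p = 4% |
|---|---|---|---|
| 500, formula (s = 0.75 to 0.5) | 2.1–2.6 | 3.2–4.2 | 5.5–7.5 |
| 500, simulated median | about 1–2 | about 2–3 | about 4–6 |
| 5,000, simulated median | 11–16 | 22–31 | 44–65 |

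At N = 500, F was below 10 in 83% to 100% of simulated samples. Solving the formula for F = 10 gives N = 9(1−p)/p ÷ (V/q). That is about 2,900, 1,400 and 690 episodes at 1%, 2% and 4% with 10 adopters, and about 4,100, 2,000 and 990 with 15.

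**Step 3. Shape of the estimates at N = 500.** The 95% range was 4 to 23 times the interquartile range, against 2.91 for a normal distribution. At 1% referral, up to 31% of samples contained no referred patient. This agrees with a Poisson count of mean 500 × 0.25 × 0.01 = 1.25, for which e^(−1.25) = 29%. The 95% Wald intervals covered 98% to 100% with either type of standard error.

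**Step 4. Coverage of 95% intervals at larger N.**

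| Setting | Robust, clinic ignored | Clustered by clinic, t reference |
|---|---|---|
| N = 5,000, 2%, 10 adopters, ICC 0.01 | 87% | 96% |
| N = 5,000, 2%, 10 adopters, ICC 0.03 | 70% | 96% |
| N = 5,000, 2%, 5 to 17 adopters | 70–91% | 93–98% |
| N = 5,000, 2%, 3 adopters | 82–94% | about 85% |
| N = 20,000 (10 or 15 adopters) | 38–70% | 92–97% |

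With 3 adopters the first-stage F ignoring clinic was about 44 but the clustered F only about 14, so it matters which one is reported.

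**The case against.** The best reply is that the plan already promises robust errors fit for 2SLS that account for the error structure of equation (3), and that structure has a site term. Read generously, this means clustering by clinic, which Step 4 shows to be adequate with 5 to 17 adopters. The reply stands in part: the plan does not say that clinic will be ignored. Equally, it does not say that clinic will be used, and an unclustered heteroskedasticity-robust run would comply with the text.

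A second reply is that 500 is a floor. The qualifying conditions in Appendix A are common, and 500 episodes over 20 clinics is only 25 per clinic. If the standard deviation of 0.01 in Section 12.3 includes binomial error, p(1−p)/0.01² implies roughly 99 (at 1%) to 384 (at 4%) eligible patients per clinic-month. This is fair, and the pooled models may well have thousands of episodes. But no expected number is given, and the diagnosis-specific models will have fewer.

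Stronger readings are tempting but not supported:
- A reader might infer that the standard errors will be wrong. The text leaves the method open; it does not fix a wrong one.
- A reader might infer that intervals will be too narrow throughout. At 500 they are too wide. They become too narrow only at larger counts, and only if clinic is ignored.
- A reader might measure instrument strength by the rise from 1% to 4%. That contrast is mainly video against onboard training, and C as defined is 1 in both phases. (The section also describes the coefficient of C as an effect of training, which should be reconciled.)
- A reader might apply the design effect 1 + (m−1)ICC. It does not fit, because the clinic indicators absorb constant clinic differences.

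**Conclusion.** The normality statement is not justified by the number of patients, and it fails at its own threshold. At 500 episodes and 1% to 4% referral, the median first-stage F is about 1 to 6 and the estimates are far from normal. With several thousand episodes the instrument is generally no longer weak at the plan's average referral near 2%, with more caution needed if adopters are few. The unstated clustering level then matters: coverage is about 70% to 87% if clinic is ignored, against about 96% if it is used (5,000 episodes, 2% referral, 10 adopters). With 3 adopters even clustered intervals cover only about 85%.

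The sizes rest on the assumed ICC, equal clinics and the 8-month windows. The mismatch between a patient count and an instrument set by clinic and period does not. The point concerns Secondary Aim 2 only and is a gap in specification, not proof that the reported intervals will be wrong.

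It is also separate from a larger difficulty: Section 12.5.5 treats activation as randomized, whereas Sections 6.2.7 and 8.1 describe voluntary adoption in one wave. Nothing proposed here cures that.

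**What to change.** In Section 12.5.5:
- Delete the sentence that derives normality from a sample above 500. State instead the expected number of episodes and of referrals, overall and per diagnosis.
- Fit a linear first stage within the 2SLS command. The section at present assigns equation (2) both to a generalized linear mixed model and to the first stage of 2SLS.
- State that standard errors are clustered by clinic with a small-cluster correction: a t reference, or a wild cluster bootstrap if adopters are few. The bootstrap was not tested here with as few as 3 adopters, so results in that case should carry a caution.
- Report the clinic-clustered first-stage F for each model, including each diagnosis-specific model.
- Give an Anderson-Rubin interval, with the same clustering, for alpha_4C and alpha_4H where F is low, and state beforehand what counts as low.

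The cost is SAP wording and standard software options; no data collection changes. The downside is wider intervals in some models, and possibly unbounded ones where the first stage is very weak.

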### 12.6 Poolability of Data

We intend to perform the primary treatment effect analysis by pooling data from all clinics. It is possible that treatment effect will differ across clinics and this will be investigated. We will fit a model with site by treatment interaction and if significant (at 0.05 level), we will present treatment effects by clinic. Although the study is not powered for detection of different treatment effects across clinics, this analysis will provide insight into possible varied treatment effects across sites or reassure that data can reasonably be pooled over sites with respect to the treatment effect.

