### 12.3 Rationale for Sample Size and Statistical Power

Sample size was established via simulation in R version 4.2.3 (R Core Team, 2023) utilizing preliminary data from clinics participating in a pilot study. This analysis is based on a within clinics, repeated measures design with two levels of EIMG exposure: Instructional Video and Onboard Training. The outcomes (e.g., referral rates) will be measured 4 times (once per month) under each level of EIMG, for a total of 8 observations per outcome per clinic. Two marginal referral rate profiles were considered in determining the sample size: a step effect of

EIMG onboarding with parallel time effect (main effects model) and a step plus accelerated time effect. A generic plot showing the two marginal rate profiles considered is presented in Figure 5.

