**Figure 5. Referral rate profiles considered in sample size analysis.**

Pilot data from 12 previously onboarded EIMG-clinics indicate the marginal referral rate (reach with eligible patients) prior to onboarding to EIMG is approximately 0.01. The following assumptions were made for both referral rate profiles. The standard deviation for the random effect of clinic, and random deviation is 0.01, the significance level for each comparison is 0.05. For the step with constant time effect, it was assumed that there was a linear change from 0.001 to 0.01 over the four months following the EIMG Instructional Video, a step-jump of 0.02, followed by a linear and parallel time effect achieving 0.04 (4%) referral rate at 8 months. For the step with accelerated time effect profile, the profile for the first 4 months was assumed to be the same as for EIMG Instructional Video with a step-jump of 0.01 followed by a linear increase to 0.04. Simulations (n=100) under each profile were conducted to compute a single empirical power, this was repeated 100 times. The power reported corresponds to the minimum empirical power observed. For a step with constant time effect a total of 10 clinics are needed to achieve a power of 92% to detect the EIMG Onboarding effect of 0.02. For the step plus accelerated time effect profile, a total of 20 clinics achieves 78% power to detect the time by EIMG status interaction when using a significance level of 0.05. Ten clinics provide 40% power to detect the step plus accelerated time effect profile.

#### 12.4 Secondary Aim 1

**To assess the effectiveness of participating in the community-based, 12-week evidence-informed PA program on EIMG-referred patient health outcomes (i.e., body weight, blood pressure, hemoglobin A1c, lipid profiles).**

*Hypothesis 1: Patients participating in the 12-week evidence-informed, community-based PA program will experience increased PA levels that is associated with a dose-response, significant reduction in body weight, systolic and diastolic blood pressure, hemoglobin A1c level, as well as improvements in their lipid profiles.*

Effectiveness is the degree to which participating in the evidence-informed PA programs improves patient physical activity levels and health outcomes (i.e., changes in cardiometabolic biometric values). Primary data for assessing effectiveness will be extracted from the Prisma

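### Section 12.6 promises clinic-level training effects only after a significant interaction in a test the plan calls unpowered, so moderate variation between clinics could often be missed and read as support for pooling.

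*Combined protocol and SAP*

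**What the plan says.** Section 12.6 opens with the pooled analysis: "We intend to perform the primary treatment effect analysis by pooling data from all clinics". It then allows for heterogeneity: "It is possible that treatment effect will differ across clinics and this will be investigated". The method is a model with a site-by-treatment interaction, and the reporting rule is "if significant (at 0.05 level), we will present treatment effects by clinic". The section next concedes that "the study is not powered for detection of different treatment effects across clinics". It nevertheless describes the analysis as giving insight into varied effects or as able to "reassure that data can reasonably be pooled over sites with respect to the treatment effect".

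The section gives no between-clinic SD of the training effect, no margin for variation that would be acceptable, and no plan for intervals on clinic-level effects. It also does not say whether the interaction model has one time trend for all clinics or a separate trend for each. Section 12.2 describes the primary model as having a random time effect within each clinic.

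Two other places bear on the point. Section 12.2 plans monthly summaries of patient-level data by clinic, with no significance condition. Section 4.14 reports large differences between clinics in past referral patterns and uses them as part of the rationale for the study.

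**The concern.** The reporting rule and the concession about power do not fit together. If the test has little power against variation that matters, p of 0.05 or more is the expected result whether or not the clinics respond alike, and it says little about whether one pooled effect describes them. Reading it as reassurance turns absence of evidence into evidence of homogeneity.

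The consequence is specific to this study. It is a multiple case study of clinics, motivated by uneven implementation despite standardized training (synopsis narrative and section 4.14). Whether onboard training raises referral by a similar amount everywhere, or a lot in some clinics and hardly at all in others, is something a health system planning scale-up would want to know. Section 12.6 commits to showing those estimates only in the case where the test happens to be significant.

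**Working it through.** **Inputs from the documents (section 12.3)**

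- Residual SD 0.01: "The standard deviation for the random effect of clinic, and random deviation is 0.01".
- Test level 0.05: "the significance level for each comparison is 0.05". Sidedness is not stated; two-sided is used for the reproduction below.
- Four months in each phase, "for a total of 8 observations per outcome per clinic".
- Mean onboarding effect 0.02.
- Number of clinics: 10 and 20 in the sample-size section. Section 6.2.7 expects several of the 20 invited clinics not to adopt.

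**Assumed input.** The between-clinic SD of the training effect (τ) is not in the documents. Values of 0.005, 0.01 and 0.02 are shown. Around a mean of 0.02, the central 95% of true clinic effects (0.02 ± 1.96τ) would be about 0.010 to 0.030, 0.000 to 0.040, and -0.019 to 0.059.

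**Step 1. Reproduce the plan's own figure.** The plan gives no power for the site-by-treatment test. Its nearest figure is 92% for the pooled step effect with 10 clinics, defined as the minimum of 100 empirical powers, each from 100 simulations. Simulating clinic effects, phase and linear time with residual SD 0.01 gives a minimum of 0.92 (mean power 0.97) when the parallel profile ends exactly at 0.04. Other readings of the profile give about 0.86 and 0.96. The error structure used below therefore agrees with the plan's. The plan's 78% and 40% concern the time-by-EIMG interaction, a different test.

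**Step 2. Variance of one clinic's estimated effect (v).**

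- Common time trend: v = 0.01² × (1/4 + 1/4) = 0.00005, so SE = 0.0071.
- Clinic-specific linear slopes: over months 1 to 8 the centred sum of squares is 2 for phase and 42 for time, with cross-product 8. Then v = 0.01² × 42 / (2 × 42 − 8²) = 0.0001 × 42/20 = 0.00021, so SE = 0.0145.

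**Step 3. Power of the F test of clinic by phase.** With n clinics, df1 = n − 1. With a common trend df2 = 6n − 1, and with clinic-specific slopes df2 = 5n. If true effects vary normally with SD τ, power = P(F > Fcrit / (1 + τ²/v)).

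- Common trend: 1 + τ²/v = 1.5, 3 and 9 for τ = 0.005, 0.01 and 0.02. Fcrit is 2.043 (n = 10) and 1.675 (n = 20).
- Clinic-specific slopes: 1 + τ²/v = 1.119, 1.476 and 2.905. Fcrit is 2.073 and 1.691.

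Chance that the test is significant:

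| Time trend | Clinics | τ = 0.005 | τ = 0.01 | τ = 0.02 |
|---|---|---|---|---|
| Common | 10 | 23% | 72% | 99% |
| Common | 15 | 29% | 86% | 100% |
| Common | 20 | 34% | 93% | 100% |
| Clinic-specific | 10 | 8% | 21% | 69% |
| Clinic-specific | 15 | 9% | 27% | 83% |
| Clinic-specific | 20 | 10% | 32% | 91% |

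Simulation with 20,000 replicates confirms the common-trend rows for 10 and 20 clinics (for example 22% and 35% at τ = 0.005). The clinic-specific rows rest on the formula.

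**Step 4. The τ needed for 50% power.** Common trend: 0.0077 with 10 clinics and 0.0060 with 20. Clinic-specific slopes: 0.0159 and 0.0125. In the last case the SD of the effect must be more than 60% of the mean effect (0.0125/0.02 = 0.63) before the test is as likely as not to detect it, even with 20 clinics.

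**Step 5. Precision of what would be reported instead.** The unshrunken 95% half-width for one clinic is 1.96 × 0.0071 = 0.014 (common trend) or 1.96 × 0.0145 = 0.028 (clinic-specific slopes).

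**The case against.** Several points on the other side are sound.

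- **The primary analysis does not depend on the test.** Section 12.6 pools in any case. No primary estimate, p-value or sample size changes through this rule.
- **Clinic differences are examined elsewhere.** Section 12.2 gives monthly descriptive summaries by clinic, sections 9.2 and 11.0 plan readiness questionnaires, staff interviews and comparisons of settings, and the section 12.2 model carries a between-cluster term for EIMG by time. A reader might infer that variation between clinics would be hidden; the documents do not support that. What is missing is narrower: estimates of each clinic's training effect, with intervals.
- **The variability cited as rationale is not the same quantity.** The synopsis narrative and section 4.14 describe differences in referral level and implementation. The interaction concerns differences in response to training. The history makes such differences plausible but does not give their size.
- **The wording is permissive.** Section 12.6 does not forbid showing clinic effects after a non-significant test, sets no formal pass or fail for poolability, and nowhere says the pooled effect will be presented as applying to every clinic. Its only commitment to show clinic effects is nevertheless conditional on significance.
- **Clinic-level intervals would be wide.** That is true, and it is also the honest description of what the data can say about a common effect.

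None of this makes a non-significant result from a test the plan itself calls unpowered into evidence that the clinics share one effect.

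**Conclusion.** The point holds in a limited form. Section 12.6 ties its only commitment to clinic-level training effects to p < 0.05 in an unpowered test, and offers the same analysis as possible reassurance. Moderate variation could often pass undetected. At τ = 0.005 the test misses it in 66-77% of trials with a common time trend and 90-92% with clinic-specific slopes. At τ = 0.01 the figures are 7-28% and 68-79%.

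A reader might infer that real variation would usually be declared poolable. That goes too far. With a common trend and τ of 0.01 or more the test is usually significant, and at τ = 0.02 it mostly is under either model. Which case applies turns on two things the documents leave open: the size of τ, and the time term in the interaction model. The random clinic time effect in section 12.2 would be expected to put power between the two sets of rows.

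The figures also assume a normal outcome with residual SD 0.01; monthly referral proportions of 1-4% may behave differently. The unsound inference from a non-significant result does not depend on any of these numbers.

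**What to change.** In section 12.6:

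1. Delete the significance condition on presenting clinic effects.
2. Delete the statement that the analysis can reassure about pooling. If a statement on poolability is wanted, base it on the estimated variation and its interval.
3. Always report clinic-specific training effects as shrunken estimates with intervals, from a model with a random clinic-by-phase effect, together with the estimated between-clinic SD of the effect and its confidence interval.
4. State whether that model uses a common or a clinic-specific time trend, since this changes the precision about twofold (0.028/0.014).

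The interaction p-value can still be given as a description. The cost is one table or plot and a short text edit, with no new data and no change to the pooled primary analysis. The drawback is imprecision: unshrunken clinic intervals of about ±0.014 to ±0.028 against a mean effect of 0.02, so the table should carry a caution against ranking clinics.
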